12.3.4. Pharmacokinetic Analysis Set

The PK Analysis Set will consist of all subjects in the Safety Analysis Set for whom at least 1 reportable PK parameter can be calculated and who have no major protocol deviations thought to impact on the analysis of the PK data.

Pharmacokinetic data for a subject during any Treatment Period may be excluded from descriptive statistics as a result of the following:

- An AE of vomiting that occurred at or before median t_{max} for that specific treatment
- The pre-dose concentration being $>5\%$ of C_{max} for an analyte in a specific treatment period

A subject may be excluded from the analysis only for the specific Treatment Period in which the above occurred. If there are no other reportable PK data for the subject, then the subject may be excluded from the PK Analysis Set.

Individual PK concentration data may be excluded from the PK analysis and/or statistical analyses and corresponding figures.

The pharmacokineticist will document and include the reason(s) for exclusion of the following:

- Exclusion of any subjects from the PK Analysis Set.
- Exclusion of any individual concentration-time points from the calculation of the PK parameters or from the statistical analyses and corresponding figures.
- Exclusion of any individual PK parameters from the statistical analyses and corresponding figures.

All available concentration data and PK parameter data will be listed for the Safety Analysis Set. Concentration or parameter data for subjects excluded from the descriptive statistics or analysis will be presented in the individual concentration versus time plots or PK parameter figures, but not in the corresponding summary figures.

12.4. Determination of Sample Size

Study sample size for a concentration-QTcF (C-QTcF)-based interval analysis is based on the recommendation from Garnett et al 2018 [21] to have 16 to 32 subjects on drug and 8 to 16 subjects on placebo. The type-1 error rate has been shown to be controlled at around 5% when the true effect is 10 ms in small-sized studies of 6 to 12 subjects with multiple measurements per subject.

A 3-period cross-over study, using C-QTcF-based interval analysis, with 2 verinurad doses and placebo in 20 evaluable healthy volunteers is expected to exceed the recommendations proposed in Garnett et al 2018 [21].

Twenty-four subjects will be randomised to a 6-sequence William's design for 3 periods and 3 treatments to achieve 20 evaluable subjects based on an expected dropout of 17%.

Evaluable subjects are defined as subjects for whom baseline and post-baseline QTcF results from smoothed dECG data are available for at least 2 treatment periods (where 1 of

the treatment periods needs to be the period in which the subject received placebo), and who have no major protocol deviation thought to impact on the analysis of the dECG data.

12.5. Protocol Deviations

Protocol deviations are considered any deviation from the CSP relating to a subject, and include the following:

- Inclusion/exclusion criteria deviations
- Dosing deviations (eg, incorrect treatment received, subject was not fasted as per the protocol requirements prior to and after dosing)
- Time window deviations for safety and/or PK assessments
- Subjects receiving prohibited concomitant medications
- Other procedural and study conduct deviations recorded by the study centre on a protocol deviation log

The criteria for the assessment and reporting of protocol deviations will be stipulated in a separate study-specific protocol deviation specification (PDS) document. This will include a WAD which stipulates tolerance windows for safety and PK assessments. Measurements performed within these tolerance windows will not be considered as protocol deviations and will not be reported.

All protocol deviations will be discussed at the data review meeting prior to database hard lock in order to define the analysis sets for the study.

Important protocol deviations will be listed by subject.

Protocol deviations (missing assessments/visits) related to COVID-19 will be listed separately.

Protocol deviations will be handled in accordance with Parexel SOPs.

For handling of protocol amendments, see Section 3.6.

12.6. Subject Disposition

A randomisation listing will be presented and include the following: each subject's randomisation number, the subject's full enrolment number, the treatment to which the subject has been randomised and the country where the study centre is located.

Subjects and/or data excluded from the PK and PD analysis sets will be listed including the reason for exclusion. Subject disposition will be summarised and will include the following information: number of subjects randomised and dosed, number and percentage of subjects completing the study and the number and percentage of subjects who were withdrawn (including reasons for withdrawal). Disposition data will be presented based on all subjects randomised.

Subject discontinuations will be listed including the date of study exit, duration of treatment and reason for discontinuation. A listing of informed consent response will also be presented.

12.7. Demographic and Baseline Data

Demographic variables (age, gender, race, ethnicity, height, weight and BMI) will be listed by subject. Demographic characteristics (age, gender, race and ethnicity) and subject characteristics (height, weight and BMI) will be summarised separately for all randomised subjects. The denominator for percentages will be the number of randomised subjects.

Medical history data will be listed by subject including visit, description of the disease/procedure, Medical Dictionary for Regulatory Activities (MedDRA) SOC, MedDRA Preferred Term, start date and stop date (or ongoing if applicable).

12.8. Prior and Concomitant Medication and Drug Administration

12.8.1. Prior and Concomitant Medication

Prior medications are those that started and stopped prior to the first dose of IMP; all medications taken after first dosing are considered as concomitant (including medications that started prior to dosing and continued after). Prior medication started within 3 months prior to the first dose of IMP will be recorded also in the concomitant medication module of ClinBase™.

Prior and concomitant medication will be listed by subject and will include the following information: reported name, preferred term (PT), the route of administration, dose, frequency, start date/time, duration and indication. Prior and concomitant medication will be coded according to the Sponsor's drug dictionary.

12.8.2. Drug Administration

Drug administration dates and times will be listed for each subject and treatment period.

12.9. Pharmacodynamic Analysis

Note: In this study, the PD data collected refer to dECG data.

Primary analysis:

A linear mixed-effect concentration-QTcF model will be used as the primary analysis. Baseline-corrected and placebo-adjusted QTcF ($\Delta\Delta\text{QTcF}$), using individual time-matched placebo for a given subject, will be the dependent variable and verinurad plasma concentrations will be the independent variable. Fixed effects will be: intercept in the absence of a treatment effect, slope of the assumed linear association between concentration and $\Delta\Delta\text{QTcF}$ and baseline QTcF. Random effects will be included on the intercept term and the slope. $\Delta\Delta\text{QTcF}$ at the concentration of interest will be estimated. A prolonging effect will be excluded if the upper bound of the two-sided 90% confidence interval for model-derived $\Delta\Delta\text{QTcF}$ is estimated to be <10 ms at the highest clinically

relevant exposure. Details of the concentration-QTcF modeling will be provided in a separate document (C-QT analysis plan).

Relevant exploratory plots will also be provided such as mean change from baseline QTcF vs. drug concentration, QTcF vs. RR and other dECG variables.

Calculations related to the PD variables will be performed by Parexel International. Parexel SOPs and Work Instructions will be used as the default methodology if not otherwise specified.

For dECGs the lead V2 is used as the primary lead, with lead V5 as the primary backup lead and lead II as the secondary backup lead, for all time points when lead V2 is found to be unsuitable for analysis or evaluation. Prior to the statistical analysis and summary, the ECG intervals will be smoothed into target time point values.

After the smoothing of QT and RR into target time point values, the HR-corrected QT will be calculated (QTcF) using the standard formula. All the statistical analyses will be performed using smoothed data.

The QTcF versus RR intervals will be plotted to confirm if HR-correction has been appropriate.

Digital ECG variables (absolute values and change from baseline for: HR, RR, PR, QRS, QT and QTcF) will be listed by subject and time point and summarised by treatment group using appropriate descriptive statistics (eg, n, geometric mean, arithmetic mean, SD, min, median, max, etc.); in addition, exploratory plots will be provided (such as time course for each dECG variable, changes from baseline for each dECG variable, by treatment group, mean with SD) and time course for $\Delta\Delta$: RR, HR, PR, QRS, QTcF for each treatment group.

The QT and QTcF outliers (defined as values following dosing that are greater than 450 ms or increases from baseline greater than 30 ms) will be summarised using cumulative counts and percentage under the following categories:

- 1 absolute value >450 ms,
- 2 absolute value >480 ms,
- 3 absolute value >500 ms,
- 4 increase from time-matched baseline >30 ms,
- 5 increase from time-matched baseline >60 ms,
- 6 absolute value >450 ms and increase from time-matched baseline >30 ms,
- 7 absolute value >500 ms and increase from time-matched baseline >60 ms.

All PD analyses will be done on the PD Analysis Set. The analysis population of the primary analysis will be defined in the C-QT analysis plan.

Additional analyses of the dECG data will be performed and a corresponding summary table will be presented according to the guidance for the analysis and review of QT/QTc interval data published by Health Canada [23].

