A linear mixed-effect concentration-QTcF model will be used as the primary analysis. Baseline-corrected and placebo-adjusted QTcF ($\Delta\Delta$ QTcF), using individual time-matched placebo for a given subject, will be the dependent variable and verinurad plasma concentrations will be the independent variable. Fixed effects will be: intercept in the absence of a treatment effect, slope of the assumed linear association between concentration and $\Delta\Delta$ QTcF and baseline QTcF. Random effects will be included on the intercept term and the slope. $\Delta\Delta$ QTcF at the concentration of interest will be estimated. A prolonging effect will be excluded if the upper bound of the two-sided 90% confidence

interval for model-derived $\Delta\Delta\text{QTcF}$ is estimated to be <10 ms at the highest clinically relevant exposure. Details of the concentration- QTcF modeling and the definition of the analysis population of the primary analysis will be provided in a separate document (C-QT analysis plan).

After the smoothing of QT and RR into target time point values, the heart rate (HR)-corrected QT will be calculated (QTcF) using the standard formula. All the statistical analyses will be performed using smoothed data. Digital ECG variables (absolute values and change from baseline for: HR, RR, PR, QRS, QT and QTcF) will be listed by subject and time point and summarised by treatment group using appropriate descriptive statistics; in addition, exploratory plots will be provided (such as time course for each dECG variable, changes from baseline for each dECG variable, by treatment group, mean with SD) and time course for $\Delta\Delta$: RR, HR, PR, QRS, QTcF for each treatment group.

Presentation and Analysis of Pharmacokinetic Data:

A listing of PK blood sample collection times, as well as derived sampling time deviations will be provided. Plasma concentrations will be summarised for the PK Analysis Set for each time point by analyte and treatment. All reportable plasma PK parameters will be listed for each subject, analyte, and treatment. A separate listing will be provided for the diagnostic PK parameters. All eligible PK data will be presented for the PK Analysis Set for each analyte (verinurad, M1, M8, allopurinol, and oxypurinol) using descriptive statistics. No inferential statistical analysis of PK parameters will be conducted.

Presentation and Analysis of Safety and Eligibility Data:

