5.2.1.3. Clinical Pharmacokinetics

Following administration of verinurad as an extended-release capsule formulation (ER8), C_{max} occurred 4 hours after dosing. Food did not affect verinurad exposure except for a 2-hour increase in time to maximum plasma concentration (t_{max}). The degree of protein binding of verinurad in human plasma was 97%. Glucuronidation is the major metabolic pathway of verinurad with oxidation as the minor pathway. The major metabolites observed in humans after oral verinurad dosing are the acyl glucuronides M1 and M8 which are renally cleared. The amount of verinurad in urine is small (<2% of given dose). The terminal half-life ($t_{1/2}$) of verinurad was 13 hours in subjects with normal renal function and 21 hours in those with moderate renal impairment. The exposure (area under the concentration-time curve [AUC] and C_{max}) of verinurad increased in a dose-proportional manner and the accumulation was minimal after once daily dosing. Subjects with an estimated glomerular filtration rate (eGFR) of 45 and 60 $\text{mL}/\text{min}/1.73\text{m}^2$ are predicted to have a 1.4 and 1.2-fold higher verinurad exposure, respectively, compared to those with normal renal function (eGFR of 90 $\text{mL}/\text{min}/1.73\text{m}^2$). Asian subjects are

predicted to have about 44% higher exposure compared to non-Asians after accounting for differences in renal function and body weight.

Further information on pharmacokinetics (PK) findings (including PK parameters of the verinurad immediate-release [IR] formulation) is available in the IB [15].

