5.3. Study Rationale and Justification of Study Design

5.3.1. Study Rationale

A prolongation of the QT and/or QTc interval can be associated with increased susceptibility to cardiac arrhythmias. Therefore, according to the ICH Guideline E14 and associated Questions and Answers (Q&A) document [20], adequate investigation of the safety of new non-antiarrhythmic drugs with systemic bioavailability should include

rigorous characterisation of their effects on ECG, with particular focus on the QT and QTc interval.

Available pre-clinical (including hERG and in vivo data), clinical ECG and event data have not indicated liability for QT-prolongation for verinurad.

The present randomised, double-blind, placebo-controlled study will follow the ICH E14 guidelines (2005) [19] and answers to question 5.1 in the associated ICH E14 Q&A document (2015) [20] with respect to assessment of the potential of the combination of verinurad and allopurinol to affect the QTc interval, where concentration-QTc (C-QTc) modeling will be used as the primary analysis [20, 21]. It is considered that the supra-therapeutic dose, if it covers at least more than twice the worst-case scenario of high exposure in patients, will provoke a detectable clinically relevant QT/QTc prolongation, even if the sensitivity/quality of the ECG analytical method is not proven to be perfect in the study. It can, therefore, be acceptable not to use an active control, provided the supra-therapeutic dose fulfills such criteria. The answer to question 5.1 of the ICH E14 Q&A document states that a separate positive control would not be necessary if there are data characterising the response at a sufficiently high multiple of the clinically relevant exposure, and this criterion is fulfilled by the supra-therapeutic exposure of verinurad anticipated in this study. A cross-over design has been chosen for practical reasons since fewer volunteers will be required and because each volunteer acts as his or her own control; intra-subject variability is therefore reduced. A single-dose cross-over design is chosen based on the PK characteristics of verinurad, allopurinol, and their metabolites. The collection of PK samples and digital ECG (dECG) recordings is time matched to allow the use of pre-specified linear mixed-effects model [21].

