5.4. Dose Rationale

A single dose of 24 mg verinurad given as the ER8 formulation to healthy subjects will give similar exposure as the highest dose tested in Phase 2b (expected therapeutic exposure) at steady state in subjects with renal impairment [15]. Subjects with impaired renal function have <2-fold higher exposure compared to those with normal renal function.

To assess the assay sensitivity, the supra-therapeutic exposure should cover at least 2× worst-case therapeutic exposure [21]. A single dose of 40 mg verinurad given as the IR formulation to healthy subjects will result in supra-therapeutic exposure (40 mg IR given to healthy subjects). The observed C_{max} and AUC following 40 mg IR to healthy subjects was 760 ng/mL and 1270 ng*h/mL, respectively, which is 10-fold higher C_{max} than worst-case clinical exposure.

Allopurinol dose of 300 mg was chosen because this is the dose given in combination with verinurad in Phase 2b.

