6. STUDY OBJECTIVES

6.1. Primary Objective

Table 6-1 Primary Objective and Outcome Measures

Primary Objectives	Outcome Measures
To assess the effect of a single dose of verinurad given as either a 24 mg ER8 formulation (therapeutic exposure) or a 40 mg IR formulation (supra-therapeutic exposure), both in combination with allopurinol 300 mg, on the QTcF interval compared to placebo using a concentration-QTcF interval analysis.	
 The primary outcome measure is $\Delta\Delta\text{QTcF}$ (derived from concentration-QTcF modeling). Parameters for this outcome measure are QTcF and C_{max}.

See Section 2 for abbreviations.

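### Does the QTcF decision rule need a stated concentration, and a planned check that the 40 mg IR exposure reached twice the worst case?

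*Combined protocol and SAP*

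**What the plan says.** - **The rule.** Section 12.9 sets one criterion: the upper bound of the two-sided 90% interval for model-derived ΔΔQTcF "is estimated to be <10 ms at the highest clinically" relevant exposure. The synopsis has the same rule: "is estimated to be <10 ms at the highest clinically relevant exposure". Section 12.9 also says that ΔΔQTcF "at the concentration of interest will be estimated". Neither phrase carries a figure in ng/mL.
- **The outcome measure.** Table 6-1 (Section 6.1) covers both verinurad treatments. It states "Parameters for this outcome measure are QTcF and" Cmax, without saying which treatment's Cmax.
- **The positive control.** Section 5.3.1 accepts having no active control "provided the supra-therapeutic dose fulfills such criteria", meaning cover of more than twice the worst-case patient exposure. It then says that "this criterion is fulfilled by the supra-therapeutic exposure of verinurad anticipated in this study".
- **The exposure figures.** Section 5.4 gives Cmax and AUC after 40 mg IR as "760 ng/mL and 1270 ng*h/mL, respectively, which is 10-fold higher" in Cmax than the worst clinical case. It also describes 24 mg ER8 as matching the top Phase 2b dose at steady state in renal impairment. Section 5.2.1.3 adds that Asian subjects are "predicted to have about 44% higher exposure compared to non-Asians", after allowing for renal function and body weight.
- **What is deferred or already reported.** Sections 12.1, 12.9 and 12.11 leave the modelling detail to a separate C-QT analysis plan, which Section 12.11 says is written prospectively. It is not among the documents. Section 12.10.3 summarises Cmax by analyte and treatment.

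**The concern.** A non-inferiority-type conclusion on QTc is only as clear as the concentration at which the model is read. Three phrases appear (the exposure in the rule, the concentration of interest, and the worst clinical case in Section 5.4), and no sentence says that they are the same point. Section 5.4 mentions renal impairment but does not say whether the Asian-subject increase is included. If the point were chosen after the data were seen, a drug with a real slope could pass at a lower concentration and fail at a higher one.

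The second worry is assay sensitivity. The high multiple replaces a positive control, yet it is declared met from exposure expected beforehand. If 40 mg IR exposure came out low in this study, a flat concentration-QTcF line would be less convincing, and no passage commits the report to saying so.

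**Working it through.** **Inputs from the documents.** Cmax 760 ng/mL after 40 mg IR and its 10-fold multiple (5.4); required multiple 2 (5.3.1, 5.4); Asian-subject factor 1.44 and renal factor 1.4 at eGFR 45 (5.2.1.3); margin 10 ms on the upper limit of a two-sided 90% interval (12.9). That limit is a one-sided 5% test, which agrees with the error rate discussed in Section 12.4.

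**Assumptions.** The documents give no variance for the model prediction, so a standard error (SE) of 1, 2 or 3 ms is assumed, equal at every concentration, with zero intercept.

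**Step 1: the implied concentration.** The worst-case Cmax is not printed separately, so the 10-fold figure can only be inverted: 760/10 = 76 ng/mL. Alternative readings:
- ten-fold higher taken as 11 times: 760/11 = 69 ng/mL;
- Asian-subject increase not yet included: 76 × 1.44 = 109 ng/mL;
- neither the renal nor the Asian-subject increase included: 76 × 1.4 × 1.44 = 153 ng/mL. This is a deliberately harsh reading, since Section 5.4 refers to renal impairment.

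**Step 2: the multiple.** Multiple = 760/C. The fall in Treatment B Cmax needed to miss 2x is 1 − 2C/760.

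| C (ng/mL) | Multiple | 2C (ng/mL) | Fall needed |
|---|---|---|---|
| 69 | 11.0 | 138 | 82% |
| 76 | 10.0 | 152 | 80% |
| 109 | 6.9 | 219 | 71% |
| 153 | 5.0 | 306 | 60% |

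**Step 3: when the choice of C alters the truth being tested.** The slope that gives exactly 10 ms is 10/C: 10/76 = 0.132 and 10/109.4 = 0.091 ms per ng/mL. Only between these slopes is the true effect below 10 ms at 76 and above it at 109. The same slopes at Treatment B give 0.091 × 760 ≈ 69 ms and 0.132 × 760 = 100 ms. With 153 as the upper candidate, the lower slope is 10/153.2 = 0.065, or about 50 ms at 760.

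**Step 4: when the choice alters the chance of passing.** P(pass) = Φ((10 − slope × C)/SE − 1.645).

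| Slope | Effect at 760 | SE | C = 76 | C = 109 |
|---|---|---|---|---|
| 0 | 0 ms | 2 | about 100% | about 100% |
| 0 | 0 ms | 3 | 95% | 95% |
| 10/760 = 0.0132 | 10 ms | 2 | 99.8% | 99.6% |
| 0.0132 | 10 ms | 3 | 91% | 89% |
| 0.05 | 38 ms | 2 | 93% | 73% |
| 0.07 | 53 ms | 1 | 99.9% | 76% |
| 0.07 | 53 ms | 2 | 76% | 32% |
| 0.07 | 53 ms | 3 | 47% | 19% |

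A drug with no effect gives the same answer at either value. A drug that adds 10 ms at the supra-therapeutic Cmax gives nearly the same answer (effects of 1.0 and 1.4 ms). Large differences need 38 ms or more at Treatment B. Section 12.9 plots QTcF change against concentration, shows ΔΔQTcF over time by treatment, and counts increases above 30 and 60 ms, so an effect of that size would be visible whichever concentration the rule used.

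**The case for a change.** The strongest case for acting is that the prediction point is part of the hypothesis, not a technical detail. It belongs beside the rule and should be fixed before data are seen. The matters that the protocol expressly sends to the C-QT plan are modelling detail and the analysis population; the clinical exposure is not named among them. If the concentration of interest were read as the Treatment B Cmax, the largest upper-bound slope that passes would drop from 10/76 = 0.132 to 10/760 = 0.0132, a tenfold difference. A comparison of the observed multiple with 2 made afterwards would also use a denominator that no one has fixed.

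Part of this stands. Section 12.9 does not cite Section 5.4, Section 5.4 does not say whether its worst case covers Asian subjects, and no sentence promises to report the observed multiple.

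The rest is weaker. The rule names a clinically relevant exposure, while the protocol labels the 40 mg IR exposure supra-therapeutic and puts it at ten times the worst case, so 760 ng/mL is not a natural reading of the rule. A worst case would ordinarily include known intrinsic factors, so 109 and 153 ng/mL rest on omissions that the text does not state. A prospective plan containing all technical details of the primary model can hardly leave out the concentration at which that model is read. Because Table 6-1 makes both treatments and Cmax part of the primary outcome, an estimate at Treatment B Cmax can fairly be expected. The observed multiple is then one division using a Cmax summary that Section 12.10.3 already requires.

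**Conclusion.** No change follows. This is a gap that analysts would fill from the same fitted model and the tables already planned. No stated rule gives a wrong result, and spelling out the concentration would alter neither the data, the model nor the criterion. The multiple stays between 5.0 and 11.0 on every reading tried, against a required 2. Even on the harshest reading, Treatment B Cmax would have to be 60% below the earlier 760 ng/mL to miss it. The choice between 76 and 109 ng/mL changes which side of 10 ms the true effect lies on only if Treatment B prolongs QTcF by about 69 to 100 ms.

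The conclusion rests on the earlier 760 ng/mL being a reasonable guide to this study, on a linear zero-intercept model, and on the assumed SEs of 1 to 3 ms. It also rests on the C-QT analysis plan being written prospectively, as Section 12.11 states; that plan was not available and could not be checked.
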